13.1. Data Collection, Processing, and Review

Good Clinical Practice Guidelines require that investigators maintain information (i.e., Source Data) in the subject's medical records, laboratory reports, clinic charts, etc. (i.e., Source Documents) that corresponds to data recorded on the Case Report Forms. In order to comply with these requirements, the following information should be maintained as source documentation, including but not limited to:

- Medical history/physical condition of the subject before enrollment
- Protocol entry criteria
- Dated and signed notes for specific results of procedures and exams
- Laboratory reports
- Information related to adverse device effects
- Surgical notes, including subject condition and re-surgery if applicable
- Quality of life assessments and TOMUS pain scales
- Discharge Summaries/Procedure reports
- Autopsy reports

Subject data will be recorded on Case Report Forms which will be provided by Boston Scientific or designated vendor. The Source Data reported on the Case Report Forms shall be derived from source documentation and shall be consistent with these source documents. Any discrepancies shall be explained and documented. Any change or correction made to the clinical data will be dated, initialed, and explained, if necessary, and shall not obscure the original entry. An audit trail shall be maintained which will be made available for review by Boston Scientific or its representative. Any queries to the data will be addressed by the study center staff in a timely manner.

13.2. Data Retention

The investigator will maintain, at the investigative site, in original format all essential study documents and source documentation that support the data collected on study subjects in compliance with ISO 14155:2011 (Clinical investigation of medical devices for human subjects - Good clinical practice). Documents must be retained for at least 2 years after the last approval of a marketing application or until at least 2 years have elapsed since the formal discontinuation of the clinical investigation of the product. These documents will be retained for a longer period of time by agreement with Boston Scientific or in compliance with other local regulations. It is Boston Scientific's responsibility to inform the investigator when

these documents no longer need to be maintained. The investigator will take measures to ensure that these essential documents are not accidentally damaged or destroyed. If for any reason the investigator withdraws responsibility for maintaining these essential documents, custody must be transferred to an individual who will assume responsibility and Boston Scientific must receive written notification of this custodial change.

14. Amendments

If a protocol revision is necessary for reasons including but not limited to, the rights, safety or welfare of the subject, or scientific integrity of the data, an amendment is required. Appropriate approvals (e.g., IRB/EC/FDA/CA) of the revised protocol must be obtained prior to implementation.

15. Deviations

An Investigator must not make any changes or deviate from this protocol, except to protect the life and physical well-being of a subject in an emergency. An investigator shall notify Boston Scientific and the reviewing IRB/EC of any deviation from the investigational plan to protect the life or physical well-being of a subject in an emergency, and those deviations which affect the scientific integrity of the clinical investigation. Such notice shall be given as soon as possible, but no later than 5 working days after the emergency occurred, or per prevailing local requirements, if sooner than 5 working days.

All deviations from the investigational plan, with the reason for the deviation and the date of occurrence, must be documented and reported to Boston Scientific. Study centers may also be required to report deviations to their IRB/EC, per local guidelines and government regulations.

Deviations will be reviewed and evaluated on an ongoing basis and, as necessary, appropriate corrective and preventive actions (including notification, center re-training, or discontinuation) will be put into place by Boston Scientific.

16. Device/Equipment Accountability

This is a post-market study and therefore no investigational devices are being used. All commercial and institutional policies regarding but not limited to device use, purchase and/or storage will be followed.

17. Compliance

17.1. *Statement of Compliance*

This study will be conducted in accordance with ISO 14155:2011 (Clinical investigation of medical devices for human subjects - Good clinical practice), ethical principles that have their origins in the Declaration of Helsinki, and pertinent individual country laws and regulations. The study shall not begin until the required approval/favorable opinion from the

IRB/EC and/or regulatory authority has been obtained, as appropriate. Any additional requirements imposed by the IRB/EC or regulatory authority shall be followed, if appropriate.

17.2. Investigator Responsibilities

The Principal Investigator of an investigational center is responsible for ensuring that the study is conducted in accordance with the Clinical Study Agreement, the investigational plan/protocol, ISO 14155:2011 (Clinical investigation of medical devices for human subjects - Good clinical practice), ethical principles that have their origins in the Declaration of Helsinki, any conditions of approval imposed by the reviewing IRB/EC, and prevailing local and/or country laws and/or regulations, whichever affords the greater protection to the subject.

The Principal Investigator's responsibilities include, but are not limited to, the following.

- Prior to beginning the study, sign the Investigator Agreement and Protocol Signature page documenting his/her agreement to conduct the study in accordance with the protocol.
- Provide his/her qualifications and experience to assume responsibility for the proper conduct of the study and that of key members of the center team through up-to-date curriculum vitae or other relevant documentation and disclose potential conflicts of interest, including financial, that may interfere with the conduct of the clinical study or interpretation of results.
- Make no changes in or deviate from this protocol, except to protect the life and physical well-being of a subject in an emergency; document and explain any deviation from the approved protocol that occurred during the course of the clinical investigation.
- Create and maintain source documents throughout the clinical study and ensure their availability with direct access during monitoring visits or audits; ensure that all clinical-investigation-related records are retained per requirements.
- Ensure the accuracy, completeness, legibility, and timeliness of the data reported to Boston Scientific in the CRFs and in all required reports.
- Record, report, and assess (seriousness and relationship to the device/procedure) every adverse event and observed device deficiency.
- Report to Boston Scientific, per the protocol requirements, all SAEs and device deficiencies that could have led to a SADE.
- Report to the IRB/EC and regulatory authorities any SAEs and device deficiencies that could have led to a SADE, if required by the national regulations or this protocol or by the IRB/EC, and supply Boston Scientific with any additional requested information related to the safety reporting of a particular event.
- Allow Boston Scientific or its designee to perform monitoring and auditing activities, and be accessible to the monitor and respond to questions during monitoring visits.

- Allow and support regulatory authorities and the IRB/EC when performing auditing activities.
- Ensure that informed consent is obtained in accordance with this protocol and local IRB/EC requirements.
- Provide adequate medical care to a subject during and after a subject's participation in a clinical study in the case of adverse events, as described in the Informed Consent Form (ICF).
- Inform the subject of the nature and possible cause of any adverse events experienced.
- Inform the subject of any new significant findings occurring during the clinical investigation, including the need for additional medical care that may be required.
- Ensure that clinical medical records are clearly marked to indicate that the subject is enrolled in this clinical study.
- Ensure that, if appropriate, subjects enrolled in the clinical investigation are provided with some means of showing their participation in the clinical investigation, together with identification and compliance information for concomitant treatment measures (contact address and telephone numbers shall be provided).
- Inform, with the subject's approval or when required by national regulations, the subject's personal physician about the subject's participation in the clinical investigation.
- Make all reasonable efforts to ascertain the reason(s) for a subject's premature withdrawal from clinical investigation while fully respecting the subject's rights.
- Ensure that an adequate investigation site team and facilities exist and are maintained and documented during the clinical investigation.
- Ensure that maintenance and calibration of the equipment relevant for the assessment of the clinical investigation is appropriately performed and documented, where applicable.

17.2.1. Delegation of Responsibility

When specific tasks are delegated by an investigator, included but not limited to conducting the informed consent process, the investigator is responsible for providing appropriate training and adequate supervision of those to whom tasks are delegated. The investigator is accountable for regulatory violations resulting from failure to adequately supervise the conduct of the clinical study.

17.3. Institutional Review Board/ Ethics Committee

Prior to gaining Approval-to-Enroll status, the investigational center will provide to the sponsor documentation verifying that their IRB/EC is registered or that registration has been

submitted to the appropriate agency, as applicable according to national/regulatory requirements.

A copy of the written IRB/EC and/or competent authority approval of the protocol (or permission to conduct the study) and Informed Consent Form, must be received by the sponsor before recruitment of subjects into the. Prior approval must also be obtained for other materials related to subject recruitment or which will be provided to the subject.

Annual IRB/EC approval and renewals will be obtained throughout the duration of the study as required by local/country or IRB/EC requirements. Copies of the Investigator's reports and the IRB/EC continuance of approval must be provided to the sponsor.

17.4. *Sponsor Responsibilities*

All information and data sent to Boston Scientific concerning subjects or their participation in this study will be considered confidential by Boston Scientific. Only authorized Boston Scientific personnel or a Boston Scientific representative will have access to these confidential records. Authorized regulatory personnel have the right to inspect and copy all records pertinent to this study. Study data collected during this study may be used by Boston Scientific for the purposes of this study, publication, and to support future research and/or other business purposes. All data used in the analysis and reporting of this study will be without identifiable reference to specific subject name.

Boston Scientific will keep subjects' health information confidential in accordance with all applicable laws and regulations. Boston Scientific may use subjects' health information to conduct this research, as well as for additional purposes, such as overseeing and improving the performance of its device, new medical research and proposals for developing new medical products or procedures, and other business purposes. Information received during the study will not be used to market to subjects; subject names will not be placed on any mailing lists or sold to anyone for marketing purposes.

17.5. *Insurance*

Where required by local/country regulation, proof and type of insurance coverage, by Boston Scientific for subjects in the study will be obtained.

18. Monitoring

Monitoring will be performed during the study to assess continued compliance with the protocol and applicable regulations. In addition, the monitor verifies that study records are adequately maintained, that data are reported in a satisfactory manner with respect to timeliness, adequacy, and accuracy, and that the investigator continues to have sufficient staff and facilities to conduct the study safely and effectively. The investigator/institution guarantees direct access to original source documents by Boston Scientific personnel, their designees, and appropriate regulatory authorities.

The study may also be subject to a quality assurance audit by Boston Scientific or its designees, as well as inspection by appropriate regulatory authorities. It is important that the

investigator and relevant study personnel are available during on-site monitoring visits or audits and that sufficient time is devoted to the process.

19. Potential Risks and Benefits

19.1. General

The risks and benefits of performing a transvaginal procedure to treat pelvic organ prolapse in the following subjects should be carefully considered due to additional risks associated with their conditions:

- Women planning future pregnancies
- Overweight women (weight parameters to be determined by the physician)
- Subjects with blood coagulation disorder
- Subjects with a compromised immune system or any other condition that would compromise healing
- Subjects with renal insufficiency or upper urinary tract obstruction

19.2. Anticipated Adverse Events

The following anticipated adverse events (AE) have been reported due to transvaginal prolapse kit placement, but are not limited to:

- Abscess
- Adhesion formation
- Allergic reaction, hypersensitivity or other immune reaction
- Bleeding
- Bruising/Hematoma
- Constipation/defecatory dysfunction
- Dehiscence of vaginal incision (Wound Dehiscence/Surgical Site Wound Irritation)
- Dehiscence and/or Necrosis
- Detrusor Instability
- De Novo Dyspareunia
- Edema/Erythema
- Exposure
- Erosion
- Extrusion
- Fistula

- Granulation tissue formation
- Hemorrhage
- Incontinence (Urinary)
- Infection/Sepsis potentiation
- Inflammation
- Irritation/Discomfort
- Migration of device from desired location
- Neuromuscular Events (including groin and leg pain)
- Organ perforation
- Overactive bladder
- Pain
- Recurrence
- Re-surgery
- Retained foreign body (foreign body reaction)
- Ureteric Injury
- Urinary Retention
- Urinary Tract Obstruction (Ureter Obstruction)
- Vessel/Nerve Injury/Perforation
- Vaginal Discharge (e.g. atypical)
- Vaginal shortening or stenosis, mesh and/or tissue contracture
- Sexual Dysfunction

19.2.1. Mesh Exposure and Erosion Event Classification

Assessment of mesh exposure and/or erosion will occur at all follow-up visits with pelvic examinations performed at 2, 6, 12, 18, 24, and 36 Months post-procedure. Identification of mesh exposure and/or erosion will occur by the medical staff member performing the pelvic exam and will be documented as an adverse event on the Case Report Forms.

19.3. *Risks Associated with Participation in the Clinical Study*

There are no additional risks with participation in this clinical study outside of the anticipated risks (see Section 19.2) for pelvic organ prolapse as conducted according to standard of care procedures.

19.4. Risk Minimization Actions

Additional risks may exist. Risks can be minimized through compliance with this protocol, performing procedures in the appropriate hospital environment, adherence to subject selection criteria, close monitoring of the subject's physiologic status during research procedures and/or follow-ups and by promptly supplying Boston Scientific with all pertinent information required by this protocol.

19.5. Anticipated Benefits

Theoretical benefits of transvaginally placed mesh for the treatment of pelvic organ prolapse may include reduction in POP symptoms.

19.6. Risk to Benefit Rationale

The use of transvaginally placed mesh has been shown to reduce recurrent prolapse following pelvic floor repair. There have been many randomized controlled trials comparing outcomes for pelvic floor repair procedures using mesh grafts to non-mesh repair. Of those studies, a reduced incidence of recurrent prolapse in the mesh-procedure group has been reported as compared to non-mesh groups.

However, the risk of mesh-related complications has been reported and can be linked to risk factors including body mass index (BMI), concomitant hysterectomy, and physician experience. There is no new literature to indicate there would be an unsatisfactory risk benefit profile for the use of transvaginally placed mesh for the treatment of POP.

20. Informed Consent

Subject participation in this clinical study is voluntary. Informed Consent is required from all subjects or their legally authorized representative. The Investigator is responsible for ensuring that Informed Consent is obtained prior to performing any study-required procedures and/or testing, or data collection.

The obtaining and documentation of Informed Consent must be in accordance with the principles of the Declaration of Helsinki, ISO 14155:2011 (Clinical investigation of medical devices for human subjects - Good clinical practice), any applicable national regulations, and local Ethics Committee and/or Regulatory authority body, as applicable. The ICF must be accepted by Boston Scientific or its designee (e.g., CRO), and approved by the center's IRB/EC, or central IRB, if applicable.

Boston Scientific will provide a study-specific template of the ICF to investigators participating in this study. The ICF template may be modified to meet the requirements of the investigative center's IRB/EC. Any modification requires approval from Boston Scientific or its designee (e.g., CRO) prior to use of the form. The ICF must be in a language understandable to the subject and if needed, BSC will assist the center in obtaining a written consent translation. Translated consent forms must also have IRB/EC approval prior to their use. Privacy language shall be included in the body of the form or as a separate form as applicable.

The process of obtaining Informed Consent shall:

- be conducted by the Principal Investigator or designee authorized to conduct the process,
- include a description of all aspects of the clinical study that are relevant to the subject's decision to participate throughout the clinical study,
- avoid any coercion of or undue influence of subjects to participate,
- not waive or appear to waive subject's legal rights,
- use native language that is non-technical and understandable to the subject or his/her legal representative,
- provide ample time for the subject to consider participation and ask questions if necessary,
- ensure important new information is provided to new and existing subjects throughout the clinical study.

The ICF shall always be signed and personally dated by the subject or legal representative and by the investigator or an authorized designee responsible for conducting the informed consent process. If a legal representative signs, the subject shall be asked to provide informed consent for continued participation as soon as his/her medical condition allows. The original signed ICF will be retained by the center and a copy of the signed and dated document and any other written information must be given to the person signing the form.

Failure to obtain subject consent will be reported by BSC to the applicable regulatory body according to their requirements (e.g., FDA requirement is within 5 working days of learning of such an event). Any violations of the informed consent process must be reported as deviations to the sponsor and local regulatory authorities (e.g. IRB/EC), as appropriate.

If new information becomes available that can significantly affect a subject's future health and medical care, that information shall be provided to the affected subject(s) in written form via a revised ICF or, in some situations, enrolled subjects may be requested to sign and date an addendum to the ICF. In addition to new significant information during the course of a study, other situations may necessitate revision of the ICF, such as if there are amendments to the protocol, a change in Principal Investigator, administrative changes, or following annual review by the IRB/EC. The new version of the ICF must be approved by the IRB/EC. Boston Scientific approval is required if changes to the revised ICF are requested by the center's IRB/EC. The IRB/EC will determine the subject population to be re-consented.

A Screening/Enrollment Log will be maintained to document select information about candidates who fail to meet the general or "other specific" entry criteria.

21. Safety Reporting

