All enrolled subjects will have an anterior and/or apical defect. Concomitant procedures to treat a secondary defect can occur (including an anterior repair, posterior repair, hysterectomy, or sling placement for stress urinary incontinence), per physician discretion. Sling placement may include a synthetic material yet a concomitant anterior repair or posterior repair cannot include a mesh implant. An anterior colporrhaphy may be required, if clinically necessary. All concomitant procedures performed will be recorded.

Subjects who undergo a medical intervention (surgical or non-surgical) to treat recurrence, persistence of POP, or a mesh or suture complication will be followed to month 36 from the initial study procedure.

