⁵Assessment of Risk Factors includes menopausal status, estrogen use, age, smoking, diabetes status, BMI, hysterectomy status, concomitant procedures, surgeon training and experience.

⁶All serious and non-serious device, procedure, and pelvic floor-related events, any other relevant events pertaining to the pelvic region, and any events resulting in death will be collected.

⁷Every effort should be made to do the follow-up visit within the window; however, if this is not possible, the site should attempt to complete the visit as soon as possible but before the next visit window opens. Follow-up visits will be considered missed once the visit window for the next follow-up visit opens. For the Month 36 visit, the visit is not considered missed until the last day of the visit window.

If a subject requires a re-surgery during the study, please refer to the reduced table below for follow-up assessments. Subjects undergoing re-interventions (non-surgical) continue with the study schedule as noted in Table 11.1-1. Additional data will be collected on subjects requiring a re-surgery, including a second procedure, mesh removal (as applicable), and second hospital discharge. All subjects who are re-operated on will continue with their follow-up schedule until 36 months post their initial study procedure.

Table 11.1-2: Data Collection Schedule for Subjects Requiring a Re-Surgery

Procedure/Assessment	Screening/ Enrollment Visit	Pre- Operative/ Baseline Visit	Surgery	Discharge	Post-Operative Follow-up Visits (± 4 Weeks)				
					Month 2 Visit (± 4 Weeks)	Re-Surgery	Discharge	Next Scheduled Follow-up Visit (-4/+12 weeks)	Month 36 Visit** (-4/+12 weeks)
Informed Consent	X							After a re-surgery, subjects will return to the clinic on the date of their next regular study visit per the Schedule of Events table above. Subjects will continue to return for all scheduled Follow-up Visits until 36 months post their initial study procedure.	
Inclusion/Exclusion Criteria Review	X								
Demographics		X							
Urine Pregnancy Test	X	X							
Physical Examination		X							
Medical History ¹		X							
Pelvic Exam with vaginal length measurement		X			X				X
Assessment of infection (vaginal, bladder)				X	X		X		X
Prolapse Grading (POP-Q Scoring)		X			X				X
PFDI-20 (Pelvic Floor Symptoms)		X			X				X
PFIQ-7 (Quality of Life)		X							X
PISQ-12 (Sexual Functioning)		X							X
PGI-I for Prolapse (Patient Improvement)									X
TOMUS Pain Scale		X			X				X

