11.4.2. Pre-Operative/Baseline Visit

The Pre-operative/Baseline Visit will occur prior to the subject having surgery. The assessments below must be completed prior to study surgery. This visit may be combined

with the Screening/Enrollment Visit and occur up to 3 months prior to surgery with confirmed absence of infection.

- Urine pregnancy test (for women of child-bearing potential only)
- Medical history and physical examination: assessment of urinary tract infection (UTI) or other vaginal infection
- Pelvic examination, vaginal length measurement
- Prolapse grading (POP-Q scoring)
- Assess baseline quality of life (PFIQ-7), sexual functioning (PISQ-12), pelvic floor symptoms (PFDI-20)
- Assess baseline level of pain (TOMUS pain scale) and analgesic use
- Assess baseline health status (EQ-5D)
- Assessment of risk factors (includes menopausal status, estrogen use, age, smoking, diabetes status, body mass index, hysterectomy status, concomitant procedures, surgeon training and expertise)

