12.2.3. Propensity Score Methodology

Analyses comparing the treatment groups will be adjusted for the propensity score. The propensity score is the probability that the subject enrolled in the mesh arm rather than the native tissue (control) arm, given the characteristics of the subject and center. The characteristics identified are as follows: age, race, body mass index, smoking, diabetes, post-menopausal, prior prolapse repair, prior hysterectomy, estrogen use, POP-Q C measurement, POP-Q Ba measurement, POP-Q Bp measurement, concomitant repair for stress urinary incontinence, and surgeon case volume. Logistic regression of both treatment arms (i.e., (transvaginal mesh repair vs. native tissue repair) on these characteristics will be used to estimate the propensity score. The subjects will then be partitioned into five strata

corresponding to quintiles of the propensity score. If the balance between treatment arms within the strata is deemed adequate, the treatment difference adjusted for propensity score stratum will be estimated as described in the following.

The propensity adjusted treatment difference will be based on averaging the treatment differences of the propensity score strata. For a binary outcome, the within-stratum treatment difference is $D_j = p_{Tj} - p_{Cj}$, where p_{Tj} and p_{Cj} is the proportion of treatment and control subjects, respectively, in stratum j . The variance of D_j is approximately

$$V_j = \frac{p_{Tj}(1 - p_{Tj})}{n_{Tj}} + \frac{p_{Cj}(1 - p_{Cj})}{n_{Cj}}$$

Denoting the number of subjects in stratum j by $n_j = n_{Tj} + n_{Cj}$, the treatment difference will be estimated by the (weighted) mean of the within-stratum treatment differences

$$D = \sum_j \frac{n_j}{n} D_j$$

where $n = \sum_j n_j$ is the total sample size across all strata and study arms. D is approximately normally distributed with variance

$$V = \sum_j \left(\frac{n_j}{n}\right)^2 V_j$$

from which a confidence interval for the true treatment difference will be constructed. For each continuous outcome, the confidence interval will be constructed similarly, with D and V obtained as above with the treatment difference within each stratum replaced by $D_j = \bar{X}_{Tj} - \bar{X}_{Cj}$, where \bar{X}_{Tj} and \bar{X}_{Cj} , respectively, is the mean of the treatment and control subjects, and

$$V_j = \frac{S_{Tj}^2}{n_{Tj}} + \frac{S_{Cj}^2}{n_{Cj}}$$

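### The propensity model omits concomitant hysterectomy and the baseline PFDI-20 and TOMUS scores, so any arm imbalance in these that remains within strata would stay unadjusted

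*Combined protocol and SAP*

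**What the plan says.** Section 12.2.3 defines the propensity score by a closed list of 14 characteristics. It opens with "age, race, body mass index, smoking, diabetes, post-menopausal, prior prolapse repair, prior hysterectomy, estrogen use, POP-Q C measurement" and ends with "POP-Q Ba measurement, POP-Q Bp measurement, concomitant repair for stress urinary incontinence, and surgeon case volume". Section 12.2.2 gives the purpose of the score as dealing with imbalance in risk factors between the arms, and requires the work to be done blind to outcomes. Section 12.1.1.3 bases both co-primary confidence intervals on this score, and Section 12.3.8.2 does the same for the 12-month interim tests.

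Elsewhere the protocol treats other variables as relevant:

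- Section 19.6 names, as risk factors linked to mesh-related complications, "body mass index (BMI), concomitant hysterectomy, and physician experience".
- The risk-factor footnote to Table 11.1-1 includes "BMI, hysterectomy status, concomitant procedures, surgeon training and experience".
- Section 8 permits concomitant procedures in both arms, "including an anterior repair, posterior repair, hysterectomy, or sling placement for stress urinary incontinence), per physician discretion".
- Section 11.4.2 lists, among the pre-operative tasks, "Assess baseline quality of life (PFIQ-7), sexual functioning (PISQ-12), pelvic floor symptoms (PFDI-20"), and a baseline TOMUS pain score.

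**The concern.** In a non-randomized comparison, stratifying on the propensity score can be relied on to balance only the covariates in the model. Of the three factors that Section 19.6 names, concomitant hysterectomy is the only one without a place on the list. Prior hysterectomy is a partial substitute: it marks women who cannot have the operation again, but among women who still have a uterus it does not separate those who have it removed from those who keep it. Concomitant procedures are not left out on principle, because stress-incontinence repair is included.

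The baseline scores raise a related but weaker question. PFDI-20 question 3 is a component of the primary composite, and pain is a secondary outcome, yet neither baseline measure is in the model.

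At stake is mainly the co-primary safety comparison. It is a non-inferiority test with a 10-point margin, so a bias that favors mesh makes a false claim of non-inferiority more likely.

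**Working it through.** **Coverage of the factors named in Section 19.6**

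- BMI: in the model.
- Physician experience: in the model through surgeon case volume.
- Concomitant hysterectomy: not in the model.

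**Whether another analysis closes the gap.** The multivariable models in Section 12.3.10 are run separately within each arm, so they do not adjust the contrast between arms. No other between-arm adjustment is specified.

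**Whether imbalance is plausible.** Hysterectomy is discretionary. Sections 8.2 and 12.2.2 assign centers as a rule to one arm, with exceptions, so local surgical habit can line up with arm. Section 8.1 expects some controls to come from the registry. No hysterectomy rate or baseline score distribution by arm is given.

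**The plan's own safety figure.** Inputs from Section 12.1.1.2 are a 14% complication rate in both arms, a 10% margin, type I error 0.05 and power 80%.

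n per arm = (1.645 + 0.842)² × 2 × 0.14 × 0.86 / 0.10² = 149, as stated. The omission does not change this number.

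**Illustration of the bias.** The inputs are assumptions, not figures from the documents: a gap between arms in concomitant hysterectomy of 20 to 40 points remaining within strata, and a 5 to 8 point effect of hysterectomy on serious complications.

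- Same effect in both arms: bias = gap × effect. This gives 0.20 × 0.05 = 1.0 point to 0.40 × 0.08 = 3.2 points, or 10% to 32% of the margin.
- Effect in the mesh arm only: the stratum weights in Section 12.2.3 use both arms together. With equal arms, the target prevalence lies halfway between the two arms, so bias = effect × gap / 2. This gives 0.5 to 1.6 points.
- No residual gap: zero.

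The size depends on the inputs. With relative risk 2, prevalence 30% against 50%, an overall rate of 14% and no true mesh effect, the base rate is 0.14 / 1.4 = 0.10. The arm rates are then 13% and 15%, a bias of 2.0 points. Letting the relative risk run from 1.5 to 3 and the gap from 10 to 40 points gives 0.6 to 6.2 points.

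**Consequence for the safety test at 149 per arm, for a bias of 1.0 to 3.2 points**

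- Mesh has fewer hysterectomies. With true rates at the margin (14% and 24%), SE = √[(0.14 × 0.86 + 0.24 × 0.76) / 149] = 0.0451. The one-sided error is Φ(bias / 0.0451 − 1.645), which rises from 5% to between 7.7% and 17.5%. For the mesh-only bias it is about 6% to 10%.
- Mesh has more hysterectomies. SE = √(2 × 0.14 × 0.86 / 149) = 0.0402. Power is Φ((0.10 − bias) / 0.0402 − 1.645), which falls from 80% to between 72% and 52%.

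**Baseline scores.** With equal variances and baseline-to-follow-up correlation r, a baseline gap shifts a change-score contrast by (1 − r) × gap. For an assumed gap of 0.2 SD and r of 0.3 to 0.7, that is 0.06 to 0.14 SD. This concerns secondary outcomes.

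**The case against.** A reader might infer that known confounders have been left unadjusted. The documents do not support that, for three reasons.

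- Confounding also needs imbalance between arms, and none is shown.
- Section 19.6 speaks of mesh-related complications. The co-primary safety endpoint counts all serious device- or procedure-related events in both arms, and the section says nothing about effectiveness. A factor that acts only in the mesh arm produces half the bias.
- Baseline PFDI-20 and TOMUS appear in no risk-factor list in the protocol. Section 11.4.2 lists them separately from its risk-factor item. They are sensible candidates, not factors that the plan itself names.

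There are also partial safeguards. Entry requires PFDI-20 question 3 of 2 or higher, which narrows the range, although three response levels remain. Chronic pain involving the pelvis is excluded. The QOL and pain scores are analyzed as improvement from baseline, and three POP-Q points cover anatomic severity. Stratification on prior hysterectomy, age and menopausal status removes part of any crude gap. The stratified estimate is used only if balance within strata is judged adequate, though no criterion is stated.

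Finally, hysterectomy belongs to the same operation and may be partly a treatment-strategy choice. The sling comparison is imperfect, because a sling treats a separate condition, stress incontinence. This is a fair reason for keeping hysterectomy out of the primary model. It is not a reason for leaving its balance unreported and its influence unexamined.

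**Conclusion.** The point holds in a limited form. Section 12.2.3 omits a factor that Section 19.6 names for mesh-related complications, and two baseline scores that the trial already collects. Any imbalance in these that remains within strata would stay unadjusted in the between-arm comparisons.

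The illustrative bias in the safety difference is 1.0 to 3.2 points with a common effect, about 0.5 to 1.6 points with an effect in the mesh arm only, and zero without a residual gap. It could favor or disfavor mesh. These figures rest wholly on the assumed gap and effect and are not estimates for this trial. The case for adding the baseline scores is one of good practice, not of inconsistency within the plan. The change is worth making because it is cheap and arm largely follows center.

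**What to change.** Before anyone has access to outcomes:

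1. Add baseline PFDI-20 (including question 3) and baseline TOMUS to the covariates in Section 12.2.3. State a rule for missing baseline scores so that no subject drops out of the logistic model. The imputation now specified covers only the efficacy composite.
2. Report the balance of concomitant hysterectomy between arms within each propensity stratum.
3. Pre-specify a second propensity model that also includes concomitant hysterectomy, as a sensitivity analysis for both co-primary endpoints. State the reason: it may be partly a treatment-strategy choice.
4. If the score has already been fitted, label every addition as a sensitivity analysis. This is a real possibility, because Table 10.1-1 puts the end of enrollment in December 2016 and the interim analysis comes 12 months after the last enrollment.

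The cost is a change of SAP wording, one extra model run, and the handling of missing baseline questionnaires. No new data collection is needed, and the stated sample size does not change.
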